13.6 Sterility Testing of EDS-EP

CCI

13.7 Columbia Suicide Severity Rating Scale (C-SSRS)

The C-SSRS (Posner et al, 2007; Posner et al, 2011) is a standardized suicidal rating system that has provided data for the pediatric suicidal risk analysis of antidepressants conducted by the Food and Drug Administration (FDA). The pediatric version of the scale will be used for patients who are less than 12 years of age at the screening visit (and will be used throughout the study, even if a patient turns 12 during the course of the study). At Screening, an assessment of suicidality will be performed using the “Baseline/Screening” version of the C-SSRS. At the baseline visit, upon admission to the clinical unit, the “Baseline” version of the C-SSRS will be performed. Follow-up assessments will be performed using the “Since Last Visit” version of the C-SSRS. Subjects with suicidal ideation will be excluded from participating in the trial.

13.8 Bone Mineral Density (BMD)

Measurements of BMD will be performed for all patients at Baseline and repeated at 6 and 12 months to assess potential steroid-related changes. Bone mass will be measured in the spine and total body (less the head), following the guidelines provided in the 2013 International Society for Clinical Densitometry Official Pediatric Position ([Gordon et al, 2014](#)). The suggested method for assessing BMD in the study is dual energy x-ray absorptiometry (DXA). The analysis will be performed with Z-scores following the above guidelines. The same method of assessment will be used for each patient throughout the study.

13.9 Tanner Staging

Assessment of physical development, sexual maturation, and the effect of treatment with dexamethasone on these aspects will be evaluated using the Tanner scale ([Marshall and Tanner 1969, 1970](#)) at Baseline, and 6 and 12 months. The scale defines physical measurements of development in children, adolescents and adults based on external primary and secondary sex characteristics, such as the size of the breast, genitals, testicular volume and development of pubic hair. Due to natural variation, individuals pass through the Tanner stages at different rates, depending in particular on the timing of puberty. Tanner staging of the breasts in pre-menarchal females and of the scrotum in males who have not completed puberty, will be performed. Post-menarchal females and males who have completed puberty will be excluded from this growth analysis.

14 REPORTING SAFETY INFORMATION

14.1 Adverse Events

Assessment of Adverse Events (AEs) will be performed throughout the study, from the time of signing of the ICF at the start of the Screening period through the final study visit (Month 12 or early discontinuation). All Adverse Events will be recorded in the CRF. In addition, all subjects will be followed up through 30 days after the final visit (Month 12 or early discontinuation) or at least 60 days after the final infusion, whichever is longer, for the occurrence of any AEs or SAEs.

14.1.1 Glossary

Adverse Drug Reaction (ADR)

In the pre-approval clinical experience with a new medicinal product or its new usages, particularly as the therapeutic dose(s) may not be established, all noxious and unintended responses to a medicinal product related to any dose should be considered adverse drug reactions. The phrase “response to a medicinal product” means that a causal relationship between a medicinal product and an adverse event is at least a reasonable possibility, i.e., the relationship cannot be ruled out.

Adverse Event (AE)

An AE is any untoward medical occurrence in a patient or clinical investigation subject administered a pharmaceutical product and that does not necessarily have a causal relationship with this treatment. An AE can therefore be any unfavorable and unintended sign (including an abnormal laboratory finding), symptom, or disease temporally associated with the use of a medicinal (investigational) product, whether or not related to the medicinal (investigational) product.

Serious Adverse Event (SAE) or Serious Adverse Drug Reaction (Serious ADR)

Any untoward medical occurrence that at any dose:

- Results in death,
- Is life-threatening, i.e., an event which, in the view of the Investigator, places the subject at immediate risk of death from the event as it occurred (it does not include an event which hypothetically might have caused death if it were more severe)
- Requires inpatient hospitalization or prolongation of existing hospitalization,
- Results in persistent or significant disability/incapacity,
- Is a congenital anomaly/birth defect (if exposure to product just before conception or during pregnancy resulted in an adverse outcome in the child), or
- Is an important medical event that may jeopardize the subject or may require medical intervention to prevent one of the outcomes listed above.

Symptoms or medically significant laboratory or instrumental (e.g., electrocardiographic) abnormalities of a pre-existing disease, such as cancer or other disease, should not be considered an adverse event. However, the occurrence of new symptoms, or laboratory or instrumental abnormalities, as well as worsening of pre-existing symptoms, are considered adverse events.

Version 1.0, 09May2015; Version 2.1, 16Nov2015; Version 3.0 (Amend. 1), 01Feb2016; Version 3.1 (Amend. 2), 28Apr2016; Version 3.2 (Amend. 3), 25May2016; Version 4.0 (Amend. 4), 29Nov2016; Version 5.0 (Amend. 5, Site-specific), 20Sep2017; Version 6.0 (Amend. 6), 29Sep2017; Version 7.1 (Amend. 7.1), Final 13 March 2018, Version 8.0 (Amend. 8.0), Final 23 April 2018; Version 10.0 (Amend. 10), Final 16 April 2019; Version 11.0 (Amend. 11), Final 24 Jun 2020

Unexpected Adverse Drug Reaction

An Unexpected Adverse Drug Reaction is an adverse event, the nature or severity of which is not consistent with the applicable product information (e.g., Investigator's Brochure for an unapproved investigational product or Package Insert/Summary of Product Characteristics for an approved product).

Non-Serious Adverse Event

A non-serious adverse event is any adverse event that does not meet the criteria listed above for a serious adverse event.

14.1.2 Data Collection

For each event, record the following information on the Adverse Event section of the Case Report Form:

- **Classification of the Event:** Classify the event as either serious or non-serious
- **Description of Signs or Symptoms:** Whenever possible, record a specific diagnosis for the event. If a diagnosis cannot be made, then record each sign or symptom separately, e.g., record nausea and vomiting as two events. If multiple episodes of an event occur, separated by an appropriate time interval to justify considering the subsequent episodes as a repeat occurrence, record each episode separately on the Case Report Form.
- **Onset Date and Time:** Record the date and time the event started. If a change from baseline/previous evaluation in a laboratory test is reported as an adverse event, record the start date as the date of collection of the first lab sample that shows the change.
- **Stop Date and Time:** Record the date and time the event resolved. If a change from baseline/previous evaluation in a laboratory test is reported as an adverse event, record the stop date as the date of collection of the first sample that shows a return to the previous level.
- **Intensity:**
 1. **Mild:** Event not resulting in disability/incapacity, which resolves without treatment.
 2. **Moderate:** Event not resulting in disability/incapacity, which requires treatment.
 3. **Severe:** Event resulting in temporary and mild disability/incapacity, which requires treatment.
- **Relationship to the Study Agent:** Every effort should be made to determine the cause of each adverse event. The correlation between the study agent and the adverse event should be classified as follows:
 1. **Probable**
 - a) The event follows a reasonable temporal sequence from administration of the study agent;
 - b) The event follows a known response pattern to the study agent;
 - c) The event cannot be reasonably explained by:
 - the known characteristics of subject's clinical state, or
 - by other therapy administered, or
 - by the diagnostic/interventional procedure;
 - d) There is evidence of partial or complete disappearance of the event after withdrawal of the product (positive de-challenge)

2. **Possible**
- a) The event follows a reasonable temporal sequence from administration of the study agent;
 - b) Causation of the event by the study agent cannot be excluded;
 - c) The event follows a known response pattern to the study agent but the event could have been produced by:
 - the subject's clinical state, or
 - other therapy administered, or
 - a diagnostic/interventional procedure.
3. **Unlikely**
- a) The adverse event follows a reasonable temporal sequence from administration of the study agent;
 - b) Other reasons are more likely to be the cause of the adverse event, based on the present knowledge of the
 - disease under treatment, or
 - other therapy administered, or
 - study drug;
 - c) A causal relationship between the adverse event and the study drug cannot be ruled out with certainty.
4. **Not Related** The event is either a pre-dose event or is definitely due to causes separate from the administration of the study agent, i.e.,
- documented pre-existing condition
 - technical and/or manual procedural problems
 - concomitant medication
 - subject's clinical state.

• **Action Taken, in relation to treatment of the AE:**

0. **None**
1. **Drug treatment required** (a medication was prescribed or changed; record on the Concomitant Medication section of the Case Report Form)
2. **Non-drug treatment required** (a non-drug treatment was prescribed or changed, record under "Comments" in the Adverse Event section of the Case Report Form)
3. **Hospitalization or prolonged hospitalization** (fill out an SAE report)
4. **Diagnostic or clinical test(s) conducted** (attach a copy of the results to the Case Report Form)
5. **Subject discontinued from the study**

- **Action taken with study treatment**

0. **Dose not changed**

1. **Drug interrupted**

2. **Drug withdrawn**

3. **Not applicable**

- **Subject Outcome:**

1. **Recovered without sequelae**

2. **Recovered with sequelae** (describe the sequelae under “Comments” in the Adverse Event section of the Case Report Form)

3. **Not Recovered, event on-going** (follow the subject until a definite outcome can be determined. When follow-up data are collected, report follow-up information under “Comments” in the Adverse Event section of the Case Report Form; if event is serious, fill in a follow-up Serious Adverse Event Report)

4. **Died** (list primary cause of death under “Event Description” of the Adverse Event section of the Case Report Form; if available, attach a copy of the autopsy report to the Case Report Form and send a copy to the Sponsor)

- **Comments:**

Provide other pertinent clinical information and observations under “Comments” in the Adverse Event section of the Case Report Form. For example, record predisposing or contributing conditions, such as previous history, concomitant diseases or medications, and/or procedural risks.

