
Investigational Medicinal Product(s): dose, mode of administration, and dosing schedule
	
The study treatment consists of one of two dose ranges of dexamethasone sodium phosphate (DSP) administered via ex vivo encapsulation into autologous erythrocytes (EDS), or an infusion of erythrocytes prepared using a placebo solution instead of a DSP solution, that are infused into the patient with AT.

	
Autologous whole blood (50 ± 5 mL) to be used for the EDS process will be collected by peripheral venipuncture into heparinized collection tubes.
 
• Group 1: EDS-EP low dose range of ~5-10 mg DSP/infusion: CCI [REDACTED]• Group 2: EDS-EP high dose range of ~14-22 mg DSP/infusion: CCI [REDACTED]• Group 3: Placebo: Patients will be treated with autologous erythrocytes prepared with the EDS process using a placebo solution CCI [REDACTED] 
Study treatment will be administered by IV infusion once per month for 12 consecutive months (6 months initial treatment + 6 months extension treatment; additional blinded unscheduled treatments will be performed in case a patient is willing to be enrolled in the open-label study IEDAT-03-2018, but the study has not yet received IRB/EC approval at the time the patient reaches Visit 15/Month 12; these unscheduled infusions will be started from the time Visit 15/Month 12 should be performed, and continuing until the site has been initiated for the open-label study IEDAT-03-2018 and he/she has been evaluated for eligibility for the study).
 
CCI [REDACTED]

Reference Therapy:
	
For patients randomized to the Placebo group, CCI [REDACTED]

Planned Treatment Duration per Patient
	
The study will consist of a 30-day Screening Period followed by two sequential (each one approximately 180-day long) treatment periods, for a total treatment duration of approximately 360 days. Patients completing the Initial Treatment Period that are doing well on their assigned treatment will have the option of continuing treatment in the Extension Treatment Period. One third of patients randomized to the Placebo group (Group 3) in the initial period that continue in the extension period will continue to receive placebo throughout the treatment

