8 STUDY OBJECTIVES

Initial Treatment Period (6 months)

Primary Efficacy Objective:

- *Efficacy:* To evaluate the effect of two dose ranges (~5-10 and ~14-22 mg DSP/infusion) of EryDex System end product [EDS-EP; the EDS is a combination product that is used to load dexamethasone sodium phosphate (DSP) into autologous erythrocytes, creating the EDS end product, which is infused into the patient], compared to placebo, on central nervous system (CNS) symptoms measured by the 'Modified' International Cooperative Ataxia Rating Scale (ICARS) in patients with ataxia telangiectasia (AT).

Key Secondary Efficacy Objective:

- To evaluate the effect of EDS-EP, compared to placebo, in this population on the Clinical Global Impression of Change from baseline (CGI-C).

Safety Objective:

- To evaluate the safety and tolerability of EDS-EP, compared to placebo, in AT patients, based on the occurrence of Treatment-Emergent Adverse Events (TEAEs), including Serious AEs and discontinuations due to AEs, and changes in vital signs, laboratory parameters, ECGs and physical/neurological examination findings.

Secondary Efficacy Objectives:

- To evaluate the effect of EDS-EP, compared to placebo, in this population on the following efficacy measures:
 - Clinical Global Impression of Severity (CGI-S) of neurological symptoms of AT;
 - Adaptive behavior measured by the Vineland Adaptive Behavior Scales (VABS).

Tertiary Objectives:

- To evaluate the effect of EDS-EP on health-related QoL using the EQ-5D-5L scale;
- To assess the pharmacokinetic and pharmacodynamic relationships between dexamethasone administered through EDS-EP and safety, tolerability, and demographic variables.
- To evaluate the pharmacokinetic (PK) profile of dexamethasone administered through EDS-EP at two dose levels based on pooled data from all patients in each treatment group. *A determination of individual PK parameters will be performed for patients with an adequate number of PK blood samples after the initial infusion.*

Exploratory Objective:

- To collect data on the use of the A-T NEST concurrent with the ICARS, CGI-S and CGI-C, as well as its use in languages other than English, and compare it with the data from the scales referenced to assess the psychometric properties of the A-T NEST.

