14.2 Safety Reporting to Investigators, IRBs/IECs, and Regulatory Authorities

The Sponsor or their designee will be responsible for reporting all SAEs to regulatory authorities, investigators, and Independent Ethics Committees / Institutional Review Boards (IRBs/IECs), as applicable, in accordance with national regulations for the United States. For all active investigators located in the United States, the Sponsor or their designee will prepare an expedited report for all SAEs that are unexpected and potentially related to the study drug, and copies will be distributed according to all applicable laws and regulations. The investigational site also will forward a copy of all expedited reports to their IRB/IEC.

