- Events with partial onset dates that indicate that the event could be treatment-emergent during the period.
- Events with completely missing onset dates.

For adverse event reporting, subject events will be allocated to the period of last treatment.

For each treatment period and over all periods, an overall summary of the number and percentage of safety population subjects having pre-treatment AEs and TEAEs will be presented by treatment received, along with the total number of TEAEs. This summary will also include the number and percentage of subjects with related TEAEs, serious TEAEs, serious related TEAEs, TEAEs leading to discontinuation, and TEAEs leading to death. Only subjects treated during the period of interest will be included in the denominator for percentages. For the summarization of AEs over all periods, treatments summarized will include EDS-EP low dose and high dose groups, non-switch placebo, placebo pre-switch, and each active treatment post-switch; placebo subjects who switch to active treatment will have only adverse events emergent during active treatment summarized.

TEAEs will also be summarized as the number and percentage of safety population subjects treated during the period (or the study overall) having any event and any event by MedDRA system organ class and preferred term. For each subject, multiple occurrences of the same event will be counted once within a system organ class and preferred term. Summaries will be prepared for the following types of events:

- TEAEs
- Related TEAEs
- Serious TEAEs
- Related Serious TEAEs
- Potentially steroid-related TEAEs
 - Low bone mineral density
 - Low CD4 count
 - Itching
 - Osteopenia
 - Osteoporosis
 - Weight gain
 - Cortisol suppression
 - Glaucoma
 - Stunt growth
 - Infections
 - Hyperglycemia
- TEAEs indicative of adrenal insufficiency per Protocol Appendix 12 and monitored by a data safety monitoring board
- TEAEs leading to discontinuation
- TEAEs leading to death
- TEAEs by maximum severity
- TEAEs by worst relationship

This summarization will be repeated for Continuous Exposure 2 subjects, and for subjects whose treatment was ended due to COVID-19.

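### The causality scale codes an adverse event definitely traced to a fault in the EDS process as Not Related, although that process is part of the investigational treatment

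*Protocol*

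**What the plan says.** **The scale.** Protocol 14.1.2 has four causality categories. Not Related applies to a pre-dose event or to one that "is definitely due to causes separate from the administration of the study agent". Four items follow, introduced by i.e. rather than e.g., and one of them is "technical and/or manual procedural problems". Possible remains open for an event that could have been produced by "a diagnostic/interventional procedure". Probable is closed when such a procedure reasonably explains the event.

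**The product.** Protocol section 8 says that "the EDS is a combination product that is used to load dexamethasone sodium phosphate (DSP) into autologous erythrocytes". Section 7.2 lists the processing equipment and disposable kit among its components. The Synopsis describes the placebo as "an infusion of erythrocytes prepared using a placebo solution instead of a DSP solution", so all three arms undergo the process.

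**Where relatedness is used.** SAP 5.4.1 summarises "the number and percentage of subjects with related TEAEs, serious TEAEs, serious related TEAEs", with matching tables by system organ class and preferred term. Protocol 14.2 provides, for US investigators, an "expedited report for all SAEs that are unexpected and potentially related to the study drug".

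**Where process faults are recorded.** SAP 5.4.9 counts potentially contaminated infusions, and SAP 5.4.10 counts process events by root cause. Neither is linked to adverse events.

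**The concern.** The scale treats a technical or manual fault as something outside the agent. That makes sense for a tablet or a vial. Here the patient's own blood is taken, processed at the site and re-infused, so a fault in the process is a fault in making the treatment. The plan itself foresees such faults: Protocol 11.6 introduces new aseptic procedures, 13.5 adds a hemolysis panel, and SAP 5.1.5 and 5.4.10 provide for interrupted processes.

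The safety objective concerns EDS-EP, not dexamethasone alone. If proven process faults are excluded from related events by definition, a statement in the study report about related harm describes something narrower than the product under test.

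**Working it through.** The plan states no figure that could be reproduced. The check applies the scale to four kinds of event and then follows the coding into the outputs.

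**Step 1: apply Protocol 14.1.2.**

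1. *Fault in the EDS process established as the cause* (for example infection from a contaminated EDS-EP, or hemolysis from a processing fault). The cause is on the Not Related list, and the requirement of certainty is met. Result: Not Related.
2. *Fault suspected but not established.* The standard "definitely due to causes separate from the administration of the study agent" is not met. Result: Possible or Unlikely.
3. *Harm from a correctly run process.* There is no procedural problem, so the clause does not apply. The rating depends on how the site reads study agent.
4. *Effect of dexamethasone itself.* The clause does not apply.

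Only the first kind is misdirected. The rule then runs the wrong way: the better a process fault is documented, the more firmly the event belongs under Not Related.

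**Step 2: check whether a definition rescues it.** The Synopsis describes the study treatment as including the processed, infused erythrocytes. The causality scale, however, refers to study agent, changes to study drug within the Unlikely category, and Protocol 14.2 also says study drug. None of these terms is stated to include or exclude the EDS process.

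**Step 3: follow the first kind of event into the outputs.**

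| Output | Event appears? |
|---|---|
| All TEAEs and serious TEAEs (SAP 5.4.1) | Yes |
| TEAEs by worst relationship (Tables 14.3.1.10.x) | Yes, as Not Related |
| Related TEAEs (Tables 14.3.1.3.x) | No |
| Related serious TEAEs (Tables 14.3.1.5.x) | No |
| Expedited report to US investigators (Protocol 14.2) | Fails the relatedness condition |
| SAE report to the CRO (Protocol 14.1.4) | Yes, whatever the relationship |
| DSMB review (Protocol 14.6) | Yes |
| Sterility and process-event counts (SAP 5.4.9, 5.4.10) | The fault is counted, but not tied to the event |

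The SAP does not say which of the four categories count as related. Any sensible cut leaves Not Related out. The SAP rule that assumes the worst relationship applies only when the field is missing, so it does not help here.

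**Step 4: exposure.** 175 randomized patients × 12 scheduled infusions = 2,100 scheduled process runs. Dropout lowers this. Repeated processes (SAP 5.1.5) and unscheduled infusions after Month 12 (Synopsis) raise it. It measures exposure and says nothing about how many events are affected.

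**The case against.** The strongest reply is that the clause is narrow and the safety net is wide. Much of this stands.

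- **The threshold is high.** Not Related needs certainty, and the glossary in 14.1.1 treats a reaction as drug-related whenever a relationship cannot be ruled out. Sites are blinded to DSP or placebo, and SAP 5.4.1 lists infections as potentially steroid-related, so certainty about sepsis would be hard to reach. A reader might infer that sites must code all process harm as Not Related, or that its related count would be zero whatever its true rate. The text does not support either.
- **Relatedness is not the only route.** SAEs go to the CRO regardless of relationship. Protocol 14.2 also makes the sponsor responsible for reporting all SAEs as applicable. The DSMB is told of SAEs and gives special emphasis to new infections. The comments field in 14.1.2 invites notes on procedural risks, and SAP 6.5 lists the process and sterility records.
- **The placebo is sound.** A reader might object that harm common to the process cancels between arms. The expected difference is indeed zero, but a process-matched placebo protects the blind and isolates the drug effect. SAP 5.4 plans no between-group safety tests, and no change to the causality scale would create a process-free arm.
- **Some text cannot be seen.** Protocol 13.6 is blacked out, and the appendices, including the action plan for positive sterility results, are not in the available text. They may deal with process harm.

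What the reply does not remove is the clause itself. An event that does meet the threshold is placed outside the related outputs, and the separate fault counts do not bring it back.

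**Conclusion.** The point holds in limited form. As written, 14.1.2 directs an adverse event definitely attributed to an EDS process fault into Not Related, and so out of the related-TEAE and related serious TEAE tables and the condition for US expedited reports. Events of uncertain cause, and harm from a correctly run process, are not forced there.

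The size cannot be given as a number, because the documents state no rate for process-caused events. It would be wrong to infer that the trial could hide such harm: the events stay in the all-event outputs and in DSMB review. What is lost is their attribution to the product.

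The conclusion assumes that sites apply the listed items literally, and that the redacted section and the appendices do not override them. It merits correction because the rule gives a wrong answer for this kind of product and the repair is cheap.

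**What to change.** **Protocol 14.1.2.** Define study agent as the whole treatment: the EDS process and kit, the EDS-EP, and its infusion. Delete the clause on procedural problems from Not Related, or limit it to procedures that have nothing to do with the EDS process. Use the same term in 14.2.

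**SAP 5.4.1.**
- State which causality categories count as related.
- Count an event as related if it is related to the drug or to the process.
- Add a summary, by arm and pooled over the arms, of TEAEs temporally linked to a positive sterility test or a logged process event. The data are already collected. The time window for the link should be fixed before unblinding, since the documents give none.

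**Events already coded.** Limit any re-query to Not Related events with such a link, and run it on blinded data.

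**Cost.** Changes to the protocol and SAP wording, one added summary and a small query round. Related-event counts may rise in every arm, including placebo, and the report should explain why.
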